4.3.2.3.3 Unsolicited Adverse Events

In addition to recording solicited reactions, parents / legally acceptable representatives will be instructed to record any other medical events that may occur from Day 0 to Day 30 or until the subject returns for the next study visit, whichever comes first. Space will be provided in the diary card for this purpose.

Information on SAEs will be collected and assessed throughout the study, from Visit 1 until 30 days after the last vaccination. Any SAE occurring at any time during the study will be reported by the Investigator in the CRB according to the completion instructions provided by the Sponsor; this includes checking the “Serious” box on the AE case report form (CRF) and completing the appropriate Safety Complementary Information CRFs. All information concerning the SAE is to be reported either as part of the initial reporting or during follow-up reporting if relevant information became available later (eg, outcome, medical history, results of investigations, copy of hospitalization reports). In case a subject experiences febrile convulsion (neurological event associating fever and seizure), the assessment will be performed according to the “Guideline for definition and collection of cases of febrile convulsion”, and this event will be considered an SAE.

For each unsolicited AE (whether serious or non-serious), the following information is to be recorded:

- Start and stop dates^a
- Intensity of the event:

For measurable unsolicited AEs that are part of the list of solicited reactions, the size of the AE as well as the temperature for fever will be collected and analyzed based on the corresponding scale used for solicited reactions (see [Table 4.1](#) and [Table 4.2](#)).

^a The stop date of all related AEs will be actively solicited. For other events, the investigator will provide the stop date when it becomes available. AEs for which no stop date was obtained during the course of the study will be considered as ongoing at the end of the study.

All other unsolicited AEs will be classified according to the following intensity scale:

- Grade 1: A type of adverse event that is usually transient and may require only minimal treatment or therapeutic intervention. The event does not generally interfere with usual activities of daily living.
- Grade 2: A type of adverse event that is usually alleviated with additional therapeutic intervention. The event interferes with usual activities of daily living, causing discomfort but poses no significant or permanent risk of harm to the research participant.
- Grade 3: A type of adverse event that interrupts usual activities of daily living, or significantly affects clinical status, or may require intensive therapeutic intervention.
- Whether the AE was related to the investigational product (for unsolicited systemic AEs)

The Investigator will assess the causal relationship between the AE and the investigational product as either “Not related” or “Related”.

- Action taken for each AE (eg, medication)

The action(s) taken by the parent / legally acceptable representative to treat and/or manage any unsolicited AEs will be classified in the CRB using the following list (all applicable items should be checked):

- None
 - Medication
 - Health care provider contact
 - Hospitalized
 - Discontinuation of study vaccination
 - Whether the AE was serious
- For each SAE, the investigator will complete all seriousness criteria that apply (outcome, elapsed time, and relationship to study procedures)
- Whether the AE caused study discontinuation

4.3.2.3.4 Adverse Events of Special Interest

An AESI is defined as event for which ongoing monitoring and rapid communication by the Investigator to the Sponsor must be done. The following AEs will be captured as AESIs throughout the study:

- Generalized seizures (febrile and non-febrile)
- Kawasaki disease
- Guillain-Barré syndrome
- Idiopathic thrombocytopenic purpura (ITP)

These events have been listed as AESIs based on the feedback received from the EU regulators.

No safety concerns relating to these AESIs have been identified with the use of MenACYW conjugate vaccine in the completed clinical trials. Because of their medical importance and to ensure expedited communication to the Sponsor, these AESIs are to be considered and collected as SAEs and reported to the Sponsor. Further instructions on the data collection for these events and the relevant definitions will be provided in the Operating Guidelines.

4.3.2.3.5 Assessment of Causality

The Investigator will assess the *causal relationship* between each unsolicited systemic AE and the product administered as either *not related* or *related*, based on the following definitions:

- Not related – The AE is clearly / most probably caused by other etiologies such as an underlying condition, therapeutic intervention, or concomitant therapy; or the delay between vaccination and the onset of the AE is incompatible with a causal relationship; or the AE started before the first vaccination (screening phase, if applicable)
- Related – There is a “reasonable possibility” that the AE was caused by the product administered, meaning that there is evidence or arguments to suggest a causal relationship

Note: By convention, all AEs reported at the injection site (whether solicited or unsolicited), and all solicited systemic AEs are considered to be related to the administered product and therefore are referred to as reactions and do not require the Investigator’s opinion on relatedness.

Adverse events likely to be related to the product, whether serious or not, that persist at the end of the study will be followed up by the Investigator until their complete disappearance or the stabilization of the subject’s condition. The Investigator will inform the Sponsor of the date of final disappearance of the event or the date of “chronicity” establishment.

4.4 Derived Endpoints: Calculation Methods

4.4.1 Safety

4.4.1.1 Solicited Reactions

4.4.1.1.1 Daily Intensity

All daily records for solicited reactions will be derived into daily intensity according to the following classification: None, Grade 1, Grade 2, Grade 3, or Missing (Unknown).

For the derivation of daily intensities, the following sequential steps will be applied:

- 1) Solicited reactions (except Fever/Pyrexia) with CRF presence recorded as “No” and with all daily records missing (Unknown) then all daily intensities will be derived as None.

- 2) For non-measurable solicited reactions, daily intensities will correspond to daily records reported in the clinical database. For measurable solicited reactions the daily measurements reported in the clinical database will be converted based upon the intensity scales defined in the protocol; this assumes a reaction that is too large to measure (non-measurable, “NM”) is Grade 3. Note the intensity could be considered “None” (not a reaction) in the analysis despite being considered a reaction by the investigator .

Note: The maximum intensity on the ongoing period is derived from the record of the maximum intensity/measurement after the end of the solicited period following the rule described above.

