12.3 Handling of Missing Data and Outliers

12.3.1 Safety

No replacement will be done.

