4.4.1.1.3 Presence

Presence is derived from the maximum overall intensity over the time period considered:

- None: No presence
- Grade 1, Grade 2, or Grade 3: Presence
- Missing or Unknown: Missing presence

Participants with at least one non-missing presence for a specific endpoint will be included in the analysis. Conversely, those without a non-missing presence will not be included in the analysis of the endpoint.

The time period is displayed as D0-D3, D4-D7, D8 and later.

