4.4.1.3.5 Adverse Events Leading to Study Discontinuation

This information will be summarized as collected. A flag is available in the clinical database for all AEs in order to identify AEs leading to discontinuation before the end of active phase.

In general, the items that are counted are:

- Disposition table: A participant who, on the “Completion at End of Study” form question “What was the participant's status?” has “Adverse Event” checked.
- Safety overview table: A participant who has either on the “Completion at End of Study” form, question “What was the participant's status?” has “Adverse Event” checked or lists a solicited AE that has “Caused Study Termination” checked that is at least Grade 1 or an unsolicited AE that has “Caused Study Discontinuation” checked that is at least Grade 1 or missing and is within the time period indicated.
- System Organ Class (SOC)/Preferred Term (PT) table: A solicited AE that has “Caused Study Termination” checked that is at least Grade 1 or an unsolicited AE that has “Caused Study Discontinuation” checked that is at least Grade 1 or missing and is within the time period indicated.

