5.3.1.3 Intensity

For solicited reactions, missing intensities will be handled as described in [Section 4.4.1.1.1](#). For unsolicited AEs, missing intensities will remain missing and will not be imputed.

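### For non-fever solicited reactions, a CRF 'No' without daily records keeps the child as a non-reactor, but a CRF 'Yes' without daily records drops the child from that endpoint

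*SAP*

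**What the plan says.** SAP 4.4.1.1.1 derives daily intensity in two steps.

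- Step 1 covers solicited reactions other than fever where the CRF presence answer is negative: "and with all daily records missing (Unknown) then all daily intensities will be derived as None".
- Step 2, for everything else, relies on what was recorded day by day: "For non-measurable solicited reactions, daily intensities will correspond to daily records reported in the clinical database". For erythema and swelling, "For measurable solicited reactions the daily measurements reported in the clinical database will be converted based upon the intensity scales defined in the protocol". A note adds that the result may be 'None' even though the investigator considered the event a reaction.

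SAP 4.4.1.1.2 takes the maximum of the daily intensities. SAP 4.4.1.1.3 turns a missing maximum into missing presence and then states: "Conversely, those without a non-missing presence will not be included in the analysis of the endpoint".

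The missing-data section adds no further rule. SAP 5.3.1.3 says "For solicited reactions, missing intensities will be handled as described in" Section 4.4.1.1.1. The general statement in Protocol 12.3.1, repeated in SAP 5.3.1, is "No replacement will be done".

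SAP 4.4.1.3.5 treats a missing grade differently by type of event. In the safety overview and SOC/PT tables, an event that ended participation is counted if it is "an unsolicited AE that has “Caused Study Discontinuation” checked that is at least Grade 1 or missing and is within the time period indicated". A solicited reaction that ended participation must be at least Grade 1.

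**The concern.** Two children can have the same empty diary for the same reaction, and the CRF presence answer alone decides what happens to them. The 'No' child is kept and counts against the reaction rate. The 'Yes' child disappears from that endpoint. The SAP does not state the second outcome in so many words; it follows from reading 4.4.1.1.1 to 4.4.1.1.3 together.

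Describing the safety profile is a stated observational objective, and solicited reactions after each dose are one of its listed endpoints. A rule that keeps recorded non-reactors but loses recorded reactors would understate those rates relative to using both recorded answers.

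The grading scales do not require this treatment. In SAP Tables 4.1 and 4.2 every non-fever reaction is at least Grade 1 once it is present; erythema and swelling start above 0 mm. Other SAP conventions lean towards counting: a reaction too large to measure is Grade 3, a missing relationship of an unsolicited systemic AE is taken as related, and an unsolicited AE with no start date at all falls within the 30-day window.

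**Working it through.** The documents state neither a reaction rate nor a rate of missing diary records, so there is no planned figure to reproduce.

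**Rule trace, all daily records from D0 to D7 missing (SAP 4.4.1.1.1 to 4.4.1.1.3)**

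| Reaction | CRF presence | Daily intensity | Derived presence | In that endpoint's analysis? |
|---|---|---|---|---|
| Not fever | No | None (step 1) | No presence | Yes, as non-reactor |
| Not fever | Yes | Missing (step 2) | Missing | No |
| Not fever | Blank | Missing (step 2) | Missing | No |
| Fever | No, Yes or blank | Missing | Missing | No |

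The asymmetry therefore concerns 8 of the 9 solicited reactions: all three injection site reactions and five of the six systemic ones.

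**Size.** Let p be the proportion of children with the reaction and m the share of them with CRF 'Yes' but no daily record. Both are assumed values. Assume also that every 'No' child is retained and no presence answer is blank.

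- Reactors still analysed: p(1-m)
- All children still analysed: p(1-m) + (1-p) = 1 - pm
- Reported rate: p(1-m)/(1-pm)
- Shortfall: p - p(1-m)/(1-pm) = pm(1-p)/(1-pm)

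For p = 30% and the 716 children planned in each of Groups 1 and 2 (SAP 5.5):

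| m | Reported rate | Shortfall (points) | Children dropped (716 × p × m) |
|---|---|---|---|
| 2% | 0.294/0.994 = 29.6% | 0.42 | 4.3 |
| 5% | 0.285/0.985 = 28.9% | 1.07 | 10.7 |
| 10% | 0.270/0.970 = 27.8% | 2.16 | 21.5 |

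Shortfall in percentage points over a wider range:

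| p | m = 1% | m = 5% | m = 10% |
|---|---|---|---|
| 10% | 0.09 | 0.45 | 0.91 |
| 30% | 0.21 | 1.07 | 2.16 |
| 50% | 0.25 | 1.28 | 2.63 |
| 70% | 0.21 | 1.09 | 2.26 |

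At m = 0 the shortfall is zero.

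**Between groups.** With equal p and equal m in both groups, the difference is unchanged. With p = 50% in both groups but m = 2% in one and 5% in the other, the rates are 0.490/0.990 = 49.495% and 0.475/0.975 = 48.718%, a spurious difference of 0.78 points.

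**Blank answers.** If a share b of non-reactors has a blank presence answer and no records, they are dropped too, and the reported rate becomes p(1-m)/[p(1-m) + (1-p)(1-b)]. This exceeds p when b is larger than m. For example, p = 30%, m = 2% and b = 5% give 0.294/(0.294 + 0.665) = 30.7%.

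**Discontinuation tables (SAP 4.4.1.3.5).** The overview table also counts any participant whose completion form gives an adverse event as the reason, so a solicited reaction of missing grade can still be picked up there. The SOC/PT table has no such route, so the reaction is lost from it.

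**The case against.** The strongest reply is that this data pattern should be rare. Staff review the diary with the parent at the visit, the site must try to clarify incomplete entries (Protocol 11.1), and missing diary data are to be clarified verbally (Protocol 13.2). That stands, and it is why the effect is probably small. It does not rule the case out. The first diary is reviewed at Visit 2, 60 to 74 days after vaccination, when a parent may recall that a reaction occurred but not its daily grades. That last step is inference.

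It can also be said that the SAP deliberately grades from records rather than from the investigator's tick-box. The note supporting this needs a recorded value that contradicts the 'Yes'. Where all daily records are missing, nothing contradicts it, and the SAP does rely on the tick-box when it says 'No'.

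Several stronger readings are tempting but not supported:

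- *Step 1 breaks the no-replacement rule.* 'No' is a recorded answer, so deriving 'None' from it uses collected data, and SAP 5.3.1.3 expressly points to this rule. The defect is that a recorded 'Yes' is not used in the same way.
- *All solicited reactions are affected.* Fever is exempt from step 1, so 'No' and 'Yes' without records are both dropped.
- *The child leaves the safety set.* The exclusion applies only to that endpoint.
- *A 'Yes' with one day recorded 'None' and the rest missing becomes a non-reactor.* SAP 4.4.1.1.2 does not say how missing ranks against 'None', so this cannot be read off the text.

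**Conclusion.** The point holds as a minor, conditional one. For the eight non-fever solicited reactions, the written rules make exclusion depend on the outcome when all daily records are missing. If such records occur, the rate is understated relative to using the recorded 'Yes': by 0.42 to 2.16 points for an assumed rate of 30% and assumed m of 2% to 10%, and by about 0.1 to 2.6 points for p from 10% to 70% and m from 1% to 10%.

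A reader might infer that the reported rates are in fact biased, or that the error is always downward. Neither follows. The documents give no value for m, and blank presence answers among non-reactors would push the rate the other way. The downward direction holds only for the comparison with a rule that uses the recorded 'Yes'.

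The safety comparison is descriptive, without hypothesis tests. The meningococcal vaccines in Groups 1 and 2 are given under a modified double blind, which makes a difference in m between those groups less likely. The primary immunogenicity result is untouched.

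**What to change.** Add a step to SAP 4.4.1.1.1, with matching text in 4.4.1.1.3 and 4.4.1.1.4. For solicited reactions other than fever with CRF presence 'Yes' and **all** daily records missing:

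- derive presence as present, with maximum intensity and time of onset missing;
- count the child in the numerator and denominator of 'any reaction' over the whole solicited period;
- show a 'grade missing' row, and leave the child out of the grade-specific and onset-period numerators;
- report the number of such cases per group.

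The trigger should be all records missing, not some. Otherwise a child with seven days recorded as 'None' and one day missing would become a reactor.

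In the safety overview and SOC/PT rules of SAP 4.4.1.3.5, count solicited reactions that caused study termination when the grade is at least 1 or missing, as is already done for unsolicited AEs. The main gain is in the SOC/PT table.

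The cost is a few lines of SAP text and minor programming, with no new data. Reported rates would be equal or slightly higher; if no such records exist, the rates do not change.

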4.4.1.1.2 Maximum Overall Intensity

Maximum overall intensity is derived from the daily intensities computed as described in [Section 4.4.1.1.1](#) and is calculated as the maximum of the daily intensities over the period considered.

4.4.1.1.3 Presence

Presence is derived from the maximum overall intensity over the time period considered:

- None: No presence
- Grade 1, Grade 2, or Grade 3: Presence
- Missing or Unknown: Missing presence

Participants with at least one non-missing presence for a specific endpoint will be included in the analysis. Conversely, those without a non-missing presence will not be included in the analysis of the endpoint.

The time period is displayed as D0-D3, D4-D7, D8 and later.

4.4.1.1.4 Time of Onset

Time of onset is derived from the daily intensities computed as described in [Section 4.4.1.1.1](#). It corresponds to the first day with intensity of Grade 1, Grade 2, or Grade 3.

Note: If a reaction is not continuous (ie, reaction occurs over two separate periods of time intervened by at least one daily intensity Missing or None) then the time of onset is the first day of the first occurrence.

Time of onset period is displayed as, D0-D3, D4-D7.

4.4.1.1.5 Number of Days of Occurrence During the Solicited Period

Number of days of occurrence over the solicited period (D0 to D7) considered is derived from the daily intensities computed as described in [Section 4.4.1.1.1](#). It corresponds to the number of days with daily intensities of Grade 1, Grade 2, or Grade 3. Number of days of occurrence on the solicited period with a specified intensity (eg, Grade 3) may also be derived.

4.4.1.1.6 Overall Number of Days of Occurrence

If a reaction is ongoing at the end of the solicited period, then the overall number of days of presence is derived from the daily intensities and the end date of the reaction after the end of the solicited period. The overall number of days of presence is:

- (End date - last vaccination date) + (number of days of presence within the solicited period) - length of the solicited period + 1

If the end date is missing or incomplete (contains missing data), the overall number of days of presence will be considered as Missing.

4.4.1.1.7 Ongoing

Ongoing is derived from the last daily intensity of the solicited period computed as described in [Section 4.4.1.1.1](#) and the maximum intensity on the ongoing period. The investigator's ongoing flag is not used because the measurement would determine the ongoing status of the reaction.

- Ongoing: if the last daily intensity of the solicited period is at least Grade 1 and the maximum intensity on the ongoing period is at least Grade 1
- Not ongoing: if the last daily intensity of the solicited period is None or the maximum intensity on the ongoing period is None.
- Missing: all other conditions (in this case, it is not included in the denominator of the ongoing analysis in the safety tables)

4.4.1.2 Unsolicited AEs

4.4.1.2.1 Presence

An observation will be considered an event if it has at least a verbatim term and is not a Grade 0 intensity event.

Grade 0 events are not included in safety analysis but are included in separate listings.

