12.1.3 Statistical Methods for Observational Objectives

Safety

Safety results will be described for subjects in all study groups. The main parameters for the safety endpoints will be described by 95% CIs (based on the Clopper-Pearson method).

It will include but is not limited to the following:

- Number and percentages of subjects reporting any solicited injection sites reactions and solicited systemic reactions occurring from Day 0 to Day 7 after each vaccination will be summarized by intensity, time of onset period, days of occurrence, and action taken.
- Number and percentages of subjects reporting any immediate unsolicited systemic AEs occurring 30 minutes after each vaccination and unsolicited AEs occurring up to 30 minutes after each vaccination will be summarized
- The number and percentage of subjects reporting any unsolicited non-serious AEs occurring up to Day 30 will be summarized by intensity, time of onset period, duration, and by MedDRA preferred term and system organ class (SOC), as well as by relationship to the study vaccine
- The number and percentage of subjects reporting at least one SAEs occurring throughout the trial will be summarized by seriousness criterion, outcome and by MedDRA preferred term and SOC, as well by relationship to the study vaccine

- The number and percentage of subjects reporting at least one of any AESIs will be summarized throughout the trial

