* For all reactions but fever, parents / legally acceptable representatives will record the intensity level (Grade 1, 2, or 3) in the diary card. For fever, they will record the body temperature, and the classification as Grade 1, 2, or 3 will be assigned at the time of the statistical analysis based on the unit used to measure the temperature and the intensity scale.

Important notes for the accurate assessment of temperature:

Parents / legally acceptable representatives are to measure body temperature once per day, preferably always at the same time. The optimal time for measurement is the evening, when body temperature is the highest. Temperature is also to be measured at the time of any apparent fever. The observed daily temperature and the route of measurement are to be recorded in the diary card, and the highest temperature will be recorded by the site in the CRB. The preferred route for this study is rectal, oral or axillary according to local practices, with the rectal route preferred for infants and the axillary route preferred for toddlers. Pre-vaccination temperature is also systematically collected by the investigator on the source document. Tympanic thermometers must not be used.

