4.4.1.2.2 Intensity

Intensity will be derived according to the following classification: None, Grade 1, Grade 2, Grade 3, or Missing

If the unsolicited AE is measurable and its preferred term is part of the list of solicited reactions, then the measurement is derived based upon and following the same rule of the intensity scales defined in the protocol for that measurable injection site or systemic reaction. Note the intensity could be considered as "None" (not a reaction) in the analysis despite being considered a reaction by the investigator .

Intensity for the other unsolicited AEs will correspond to the value reported in the CRF.

The maximum intensity corresponds to the highest intensity for a unique term.

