4.4.1.2.6 Serious Adverse Events

An event will be considered as a serious event if “Yes” is checked for “Serious” in the CRF.

SAEs will be analyzed throughout the study using the following periods:

- Within 7 days
- Within 30 days
- During the study (ie, all SAEs occurred during the study)
- From D31 after vaccination injection to next visit (for SAE overview only)

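### SAP 4.4.1.2.1 leaves Grade 0 unsolicited events out of the safety analysis with no exception for serious ones, so an SAE coded to Pyrexia with a recorded temperature below 38.0°C would be listed but not tabulated

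*SAP*

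**What the plan says.** SAP 4.4.1.2.1 (Presence, unsolicited AEs) sets the entry condition: "An observation will be considered an event if it has at least a verbatim term and is not a Grade 0 intensity event". It then adds: "Grade 0 events are not included in safety analysis but are included in separate listings". Neither sentence mentions seriousness.

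SAP 4.4.1.2.2 (Intensity) covers grading by measurement: "If the unsolicited AE is measurable and its preferred term is part of the list of solicited reactions", the grade is derived from the measurement on the solicited-reaction scale. The section accepts that the result may be 'None' "in the analysis despite being considered a reaction by the investigator". In SAP Table 4.2 the lowest fever grade begins at 38.0°C.

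Two places describe the SAE output without any intensity condition. SAP 4.4.1.2.6 names as an analysis period "During the study (ie, all SAEs occurred during the study"). Protocol 12.1.3 states: "The number and percentage of subjects reporting at least one SAEs occurring throughout the trial will be summarized".

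**The concern.** Seriousness and intensity are separate attributes, and SAP 4.3.2.1 says so. An admission to hospital makes an event serious whatever the thermometer showed. Under the rule as written, a derived intensity decides whether a serious event is counted at all.

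At stake is the completeness of the SAE tables. SAE counts per group are usually small integers, so one missing child is visible. A reader who finds an SAE in the listing but not in the table would have no stated reason for the difference, because SAP 5.7 (changes to planned analyses) does not mention the exclusion.

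The SAP also shows that it knows how to protect serious events. SAP 4.4.1.2.4 drops late-onset events from the analysis only when they are non-serious, non-AESI and non-MAAE. The Grade 0 rule lacks that limit, which looks like an omission rather than a decision.

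**Working it through.** The plan gives no figure to reproduce, so the check follows one record through the derivation rules. Take a child admitted to hospital with fever that begins on Day 8 or later, outside the solicited window. The preferred term is Pyrexia, the highest recorded temperature is below 38.0°C, and the Serious box is ticked.

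1. SAP 4.3.2.1: an event leading to hospitalisation is an SAE, unless the admission was planned before inclusion or treatment was outpatient only. SAEs are a subset of unsolicited AEs. The unsolicited-AE rules therefore apply.
2. SAP 4.4.1.2.2: fever is measurable and Pyrexia is on the solicited list, so intensity comes from the recorded temperature.
3. SAP Table 4.2: Grade 1 starts at 38.0°C, so the derived intensity is 'None'.
4. SAP 4.4.1.2.1: a Grade 0 observation is not an event and is only listed. The SAP never states that 'None' is Grade 0. However, 'None' is the category below Grade 1 in 4.4.1.2.2, and the scale for other unsolicited AEs runs only from Grade 1 to Grade 3, so nothing else in the derivation corresponds to Grade 0.
5. SAP 4.4.1.2.6: a serious event is an event with Serious ticked. The record stopped being an event at step 4, so it is not a serious event in the tables.

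Two comparisons show that the outcome is inconsistent.

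| Record | Derived intensity | SAE tables |
|---|---|---|
| Pyrexia, Serious = Yes, temperature below 38.0°C | None | Out, listed only |
| Pyrexia, Serious = Yes, no temperature recorded | Missing | In |

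| Exclusion rule | Serious events protected? |
|---|---|
| Late onset (SAP 4.4.1.2.4) | Yes |
| Grade 0 (SAP 4.4.1.2.1) | No |

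**Which terms are reached.** The measurable solicited reactions are fever, injection site erythema and injection site swelling. Grade 1 for the last two starts above 0 mm (SAP Table 4.1), so only a recorded 0 mm would give 'None'. In practice the rule bites on fever.

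**Discontinuations (SAP 4.4.1.3.5).** The disposition table counts by the end-of-study form, with no grade condition. The safety overview counts a participant through that form or through a flagged AE that passes the grade condition. The SOC/PT table uses only the flagged AE, and an unsolicited one must be at least Grade 1 or missing. A child who left because of a Grade 0 event, with Adverse Event given as the end-of-study status, is therefore in the first two tables but not in the third.

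**Size per child.** Assume that the safety set equals planned enrolment (716 in each of Groups 1 and 2, 110 in each of Groups 3 and 4). One child dropped lowers the SAE percentage by

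- Group 1 or 2: 1/716 = 0.14 percentage points
- Group 3 or 4: 1/110 = 0.91 percentage points

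The documents give no basis for the number of such children, and zero is possible. If one assumes 0 to 5 in the whole trial, the extreme with all five in one group is 5/716 = 0.70 points or 5/110 = 4.5 points.

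**The case against.** The strongest reply is that the specific section should govern. SAP 4.4.1.2.6 speaks of all SAEs during the study, and SAP 4.4.1.3.2 says that seriousness is summarised without derivation. A programmer could reasonably follow those and keep the record. This stands as evidence of intent, and it is why the point is that the sections must be reconciled, not that such SAEs are certain to disappear. It does not remove the conflict, since neither section is written as an exception to 4.4.1.2.1.

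Several stronger readings are tempting, and the documents do not support them.

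- *Grading by temperature is an undeclared change from the protocol.* Protocol 9.3.2.3.3 already provides that measurable unsolicited AEs on the solicited list are analysed on that scale. Only the exclusion step is new.
- *The single fever threshold is the fault.* The same cutoff applies to every route, with the "rectal route preferred for infants and the axillary route preferred for toddlers". That is the protocol's own fever definition (Protocol Table 9.5) and is not at issue here.
- *Discontinuations due to AEs are understated throughout.* Only the SOC/PT table depends wholly on the grade condition.
- *AESIs would be lost.* None of the four listed in SAP 4.3.2.3.4 (generalised seizures, Kawasaki disease, Guillain-Barré syndrome, ITP) is a measurable solicited term. Febrile convulsion is assessed separately and is always an SAE.
- *Database reconciliation or safety reporting would fail.* Protocol 11.2 reconciles two databases, and the record stays in both. Only the tables are affected.

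The rarity argument also stands. The term must be Pyrexia and not an infection or other diagnosis, a sub-threshold temperature must be on record, and the child must have no other SAE for the subject count to change. That limits the effect but does not make the rule correct.

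**Conclusion.** The point holds in a limited form. Followed literally, the SAP removes from its SAE tables a serious fever event with a recorded temperature below 38.0°C. This contradicts its own SAE section and the protocol's commitment, and it treats serious events differently from the late-onset rule. The conclusion rests on one reading, that derived 'None' is what 4.4.1.2.1 calls Grade 0.

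The size is small. No case may ever arise, safety is descriptive with no hypothesis test, and each affected child remains visible in a listing. The per-child effect of 0.14 or 0.91 points assumes planned enrolment, and any count of children is an assumption. It is still worth correcting before the tables are produced, because it is a stated rule that can give a wrong SAE count.

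**What to change.** In SAP 4.4.1.2.1, limit the Grade 0 exclusion to non-serious events that did not cause study discontinuation, so that every record with Serious = Yes enters the SAE tables whatever its derived intensity. State there that 'None' in 4.4.1.2.2 and 'Grade 0' mean the same thing.

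In SAP 4.4.1.3.5, change the unsolicited-AE condition of the SOC/PT table in the same way, so that a flagged Grade 0 event which caused discontinuation is counted there too. Record the clarification in SAP 5.7.

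The cost is a few sentences and a condition in each of the two derivations. The one small downside is that retained events have no place in tables by intensity, so those tables need a 'None' row. No threshold, endpoint or data collection changes.
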